3.5.4 Safety assessments

Safety assessments will consist of monitoring and recording all adverse events and serious adverse events, the regular monitoring of hematology, blood chemistry (including liver enzymes) and urine values, regular measurement of vital signs and the performance of physical examinations and ECG.

Adverse events

Information about all adverse events, whether volunteered by the subject, discovered by investigator questioning, or detected through physical examination, laboratory test or other means, will be collected and recorded in the patient's source documents and CRF and followed as appropriate.

An adverse event is any undesirable sign, symptom or medical condition occurring after starting study drug(s) (or therapy) even if the event is not considered to be related to study drug (or therapy). Study drug (or therapy) includes the drug (or therapy) under evaluation, and any reference or placebo drug (or therapy) given during any phase of the trial.

Medical conditions/diseases present before starting study treatment are only considered adverse events if they worsen after starting study treatment. Adverse events occurring before starting study treatment but after signing the informed consent form are recorded on the Medical History/Current Medical Conditions Case Report Form. Abnormal laboratory values or test results constitute adverse events only if they induce clinical signs or symptoms or require therapy, and are recorded on the Adverse Events Case Report Form under the signs, symptoms or diagnosis associated with them.

As far as possible, each adverse event will also be described by:

1. its duration (start and end dates),
2. the severity grade (mild, moderate, severe)
3. its relationship to the study drug (suspected / not suspected),
4. the action(s) taken and, as relevant, the outcome.

Examples of the severity grade, relationship to study drug and actions taken, as presented in the case report form are provided in Section 8.1.3, Instructions for completing Adverse Event Case Report Forms.

Pre-defined safety and tolerability parameters

The following pre-defined safety and tolerability conditions are known side effects of valsartan and nateglinide and will be recorded on the CRF.

Valsartan

Hypotension

Hypotension is defined as the mean of 2 sitting diastolic or systolic blood pressure measurements of < 60 mm Hg or < 100 mm Hg, respectively.

Orthostatic hypotension

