Samples for spot urine albumin and creatinine will be taken at Visit 1 and analyzed for eligible patients, only (one measurement must be available prior to randomization). Following randomization, spot urine albumin and creatinine will be measured annually and at the final visit.

Vital signs

Notable ranges for vital signs are provided in Appendix 3.

Height

Height will be measured at Visit 1.

Pulse rate

Pulse rate will be measured at each visit once in the sitting position after 5 minutes resting followed by one measurement in the standing position after at least 2 minutes of equilibration. Pulse rate will be measured for 30 seconds and before blood pressure measurements.

Blood pressure

Systolic and diastolic blood pressure will be measured at each visit using a validated device (two measurements in the sitting position after 5 minutes resting followed by one measurement in the standing position after at least 2 minutes of equilibration). Blood pressure will be measured by the same clinician using the same device on the patient's dominant arm. The measurements should always be carried out at the same time of the day and prior to the intake of the morning doses.

Body weight

Body weight will be measured to the nearest 0.1 kilogram in indoor clothing but without shoes at each visit using the same scale.

Waist circumference

Waist circumference (the minimum circumference of the waist above the iliac crest) will be measured at Visit 1, yearly thereafter and at the final visit.

Physical examination

A physical examination will be performed at Visit 1, yearly thereafter and at the final visit. Physical examination evaluations should include general appearance, skin, neck (including thyroid), eyes, ears, nose, throat, lungs, heart, abdomen, back, lymph nodes, extremities, and neurological (including sensory) examinations. Information about the physical examination must be present in the source documentation at the study site. Significant findings present prior to randomization will be entered in the Relevant Medical History/Current Medical Conditions Case Report Form at Visit 2. Significant findings made after the start of the study which meet the definition of a pre-defined or serious adverse event (as defined in Section 3.5.4) will be recorded on the Adverse Event Case Report Form.

Electrocardiogram

A standard 12 lead electrocardiogram (ECG) must be obtained at Visit 2, Month 36, and at the final visit.

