6.1.6 Safety evaluation

The assessment of safety will be based mainly on the frequency of all adverse events and on the number of laboratory values that fall outside of pre-determined ranges. Other safety data (e.g. electrocardiogram, vital signs, special tests) will be considered as appropriate.

Adverse events will be summarized by presenting, for each treatment group, the number and percentage of patients having any adverse event, having an adverse event in each body system and having each individual adverse event. Any other information collected (e.g. severity or relatedness to study medication) will be listed as appropriate.

For the subset of patients at prospectively defined study centers who will be dispensed glucometers, the number and percentage with confirmed hypoglycemic events (plasma glucose < 3.3 mmol/l) will be presented. The number and percentage of patients with any events suggestive of hypoglycemia will also be presented for this subset, in order to be able to put the number of confirmed vs. suggestive events into a perspective. Patients who were dispensed glucometers at the investigator's discretion (i.e. not from the pre-defined centers) will not be shown in this summary.

Laboratory data will be summarized by presenting shift tables using extended normal ranges (baseline to most extreme post-baseline value), by presenting summary statistics of raw data and change from baseline values (means, medians, standard deviations, ranges) and by the flagging of notable values in data listings.

Data from other tests (e.g. electrocardiogram or vital signs) will be listed, notable values will be flagged, and any other information collected will be listed as appropriate.

Unless otherwise indicated, the safety population will be used for the safety analyses.

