8.1.3 Instructions for completing adverse event case report forms

All adverse events are to be reported on an Adverse Event Case Report Form. Refer to the Case Report Form or to the Case Report Form Completion Guideline for details.

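### The physical-examination paragraph of Section 3.5.4 routes a narrower set of findings to the Adverse Event CRF than Sections 3.5.4, 8.1.3 and 6.1.6 assume, so adverse event frequencies could be incomplete and vary by site

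*Protocol*

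**What the plan says.** Four places in the protocol bear on what reaches the Adverse Event CRF.

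- **Section 3.5.4, Physical examination.** After study start, the significant findings that go forward are those "which meet the definition of a pre-defined or serious adverse event", and these "will be recorded on the Adverse Event Case Report Form". Information about the examination must otherwise be present in the source documentation at the site.
- **Section 3.5.4, Adverse events.** The scope is "Information about all adverse events, whether volunteered by the subject, discovered by investigator questioning, or detected through physical examination, laboratory test or other means". Events "detected through physical examination, laboratory test or other means, will be collected and recorded in the patient's source documents and CRF" are therefore covered by name.
- **Section 8.1.3.** "All adverse events are to be reported on an Adverse Event Case Report Form". For details it points to the CRF and its completion guideline.
- **Section 6.1.6.** "The assessment of safety will be based mainly on the frequency of all adverse events", and also on the number of laboratory values outside set ranges. The tables give patients with any event, with an event in each body system, and with each individual event.

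The pre-defined conditions are listed in Section 3.5.4. For valsartan they are four forms of hypotension (by measurement, orthostatic, symptomatic, and orthostatic symptomatic). For nateglinide they are symptoms suggestive of hypoglycemia and confirmed hypoglycemia.

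**The concern.** The examination paragraph selects by category of adverse event. The other three places do not. The examination covers skin, eyes, lungs, abdomen, lymph nodes, extremities, the nervous system and more, and most new findings there will be neither hypotension nor hypoglycemia, and many will not be serious. The examination paragraph is also the only one written specifically about handling examination findings, so a site that follows it can fairly say it obeyed the protocol.

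At stake is one of the two main safety measures. If some of the 800-900 planned centers record every examination finding that is an adverse event and others record only the narrower set, the body-system and individual-event tables will mix two recording rules. Section 8.2.2 asks monitors to verify the recording of safety variables, but the protocol gives them two standards to verify against.

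**Working it through.** There is no figure in the plan to reproduce, and no arithmetic applies to the contradiction itself. The check is to take types of event and ask what each paragraph requires.

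| Event after study start | 3.5.4 Physical examination | 3.5.4 Adverse events and 8.1.3 | Conflict? |
|---|---|---|---|
| Serious, found at examination | Adverse Event CRF | Adverse Event CRF | No |
| Hypotension or hypoglycemia, non-serious, found at examination | Adverse Event CRF | Adverse Event CRF | No |
| Other, non-serious, volunteered or found by questioning | Does not apply | Adverse Event CRF | No |
| Other, non-serious, found only at examination | Not directed to the form | Adverse Event CRF | **Yes** |

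(Section 3.5.4, Adverse events, says CRF; Section 8.1.3 specifies the Adverse Event form.)

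The conflict lies in one row. An example is a new skin or sensory finding that meets the adverse event definition, is not serious, and was noticed only because the patient was examined.

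**How often the row can arise.** Table 3 and Section 3.5.4 place the examination at Visit 1, yearly and at the final visit. Table 3 schedules adverse event collection at every visit after baseline, including the six-monthly ones. Many events that an examination would show can therefore also be picked up by asking the patient.

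**What an omission would do to the Section 6.1.6 tables.** For one type of event, let p1 and p0 be the true proportions of patients with it on and off a drug. Let f be the proportion of those patients whose event goes unrecorded, assumed the same in both groups because the trial is double-blind. The recorded proportions are (1 − f)p1 and (1 − f)p0. Their difference is (1 − f)(p1 − p0), and their ratio is still p1/p0. So the recorded frequency and the absolute difference both fall by the fraction f for that type of event, and the ratio does not change.

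The value of f depends on how many events of that type are found only at examination and on how many sites read the paragraph narrowly. The protocol gives neither, so f cannot be given a value or a defensible range. It would also differ by type of event. It may be near zero for the count of patients with any adverse event, since a patient with another recorded event is still counted.

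**The case against.** The best defence is that the examination paragraph contains no word such as *only* and forbids nothing. A site that records every adverse event satisfies all the passages at once. The general rule is stated twice, once with physical examination named as a source. Section 8.1.3 also refers sites to the CRF completion guideline, which is not at hand and may settle the matter. All of this stands. It means that loss of events is possible, not established.

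It does not remove the conflict. The clause is restrictive as written, and its cross-reference to Section 3.5.4 picks out a subset of adverse events. If everything was to be recorded, the clause has no purpose.

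Three stronger readings are tempting, and the documents support none of them:

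- *That safety data will be incomplete.* This assumes that sites follow the narrower sentence against two explicit general rules. Nothing in the protocol shows which they follow.
- *That the loss can be sized from the number of yearly examinations, or from an assumed share of all events.* The first counts examinations, not lost events. The second is a share of all events, whereas a risk difference depends on what is lost from the excess between groups.
- *That all adverse events are the sole main safety measure.* Section 6.1.6 names laboratory values beside them.

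**Conclusion.** The contradiction is real and should be corrected. The examination paragraph of Section 3.5.4 directs a narrower set of events to the Adverse Event CRF than the Adverse events paragraph of the same section and Section 8.1.3 require, and than Section 6.1.6 analyses. The consequence is conditional: if some sites read the paragraph as a restriction, non-serious events outside the pre-defined list and found only at examination could be missing, and frequencies could vary by site. The size is unknown and cannot be derived from the protocol. Under the double blind there is no stated reason for the loss to differ between treatment groups. The likely effect is lower recorded frequencies and smaller absolute differences for the affected types of event, with no evident bias towards one group. The efficacy analyses and the error rate are not touched.

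**What to change.** Reword the sentence under Physical examination in Section 3.5.4 so that any significant new or worsened finding that meets that section's adverse event definition is recorded on the Adverse Event CRF, and inform sites. Check that the CRF completion guideline says the same.

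If selective collection was intended, leave that sentence and correct the Adverse events paragraph of Section 3.5.4, Section 8.1.3 and Section 6.1.6, so that the analysis does not claim to cover all adverse events.

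The cost is one sentence in an amendment, a site memo and a few more CRF entries. There is one side effect. This version of the protocol post-dates the December 2005 interim analysis, about four years into the study, so sites that had used the narrower reading would change their recording mid-trial. Early and late adverse event rates at those sites would then not be fully comparable, and the study report should say so when it presents them.

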3.5.5 Other assessments

Screening visit (Visit 1) information

The following information will be collected at Visit 1: demographics, vital signs, waist circumference, concomitant medication, medical history. In addition, laboratory measurements will be performed. All information except medical history, concomitant

medication, and laboratory measurements will be collected using IVRS. Also, the decision to randomize or discontinue the subject from screening, including the reason for discontinuation, will be recorded using IVRS. All Visit 1 screening information will be transferred from IVRS to the trial database.

2hr OGTT (with FPG, post-prandial glucose)

Subjects have to be fasting at each OGTT assessment. A fasting and 2hr post-challenge glucose evaluation is required at Visit 1 to confirm eligibility of screened subjects. Post-randomization OGTT will be performed at Visit 7 (Month 12), annually thereafter, and at the final visit (for exceptions see below). Repeat OGTT to confirm a glycemic endpoint will be performed as soon as possible (on a different day), preferably within 4 weeks (≤ 28 days) but no later than 12 weeks (≤ 84 days) following the day of the initial laboratory assessment that indicates diabetes. If, for whatever reason, a repeat OGTT cannot be performed, at least an FPG should be performed at that time.

For patients who have progressed to diabetes and have had an FPG ≥ 300 mg/dL (16.7 mmol/L), an annual OGTT is no longer required; an FPG, however, should still be performed. An annual OGTT is still required for all patients with FPG < 300 mg/dL.

In patients who have progressed to diabetes HbA_{1c} will be measured at time point 0 minutes of positive, confirmatory OGTT and annually thereafter.

Patients who achieved a confirmed glycemic endpoint must withhold the morning dose of any antidiabetic treatment, in addition to the study medication, prior to each subsequent OGTT assessment.

The OGTT must initiate (0 minute sample) no later than 10:00 a.m.

Subjects are given a 75 gram glucose-equivalent oral glucose challenge. The glucose solution is centrally provided to all centers. A venous sample will be taken 2 hours post-challenge to evaluate glucose levels (see table below).

Table 5 OGTT assessment

	Time (minutes) Post Glucose Administration	
	0+	120
75 g glucose	X	
Plasma glucose	X	X
HbA _{1c} ++	X	

Life-style intervention education

At Visit 2 and every visit thereafter, patients will receive counseling on diet and physical activity as treatment to prevent diabetes. Counseling will include review of an education brochure. The assessment of physical activity will include the use of pedometers. Pedometers will be dispensed to a subset of patients based on practical considerations. At Visit 2 and every visit thereafter, information on life-style conduct, including physical activity and diet habits, will be assessed.

Health economics assessment

Health economics assessments will be performed at Visit 2, every 6 months thereafter and at the final visit. The assessment will include information on hospitalization (diagnosis, admission, discharge date), medical care in addition to this protocol, and the patient's health state using a visual analogue scale (VAS).

The VAS forms provided in the CRF will be in English only. However laminated VAS forms in local languages will be available to each center separately. Patients should read the instructions on the laminated forms, in their native language, prior to completing the VAS form in the CRF by drawing a line through the VAS to indicate their health status on the day of the visit. The investigator should then record the VAS score in the appropriate space provided.

The analysis of health economic parameters will be reported separately.

Pharmacogenetic assessments

The pharmacogenetic assessment is also detailed in the Substudy 1 Protocol for countries where this assessment is required to be separate from the core protocol.

In order to begin to study the effects of human genetic variation on drug responses, it is planned to conduct exploratory pharmacogenetics research studies as a part of this protocol. The objective is to identify genetic factors related to impaired glucose tolerance and cardiovascular disorders that may predict response to treatment with nateglinide and/or valsartan and/or predict the subject's relative susceptibility to drug-drug interactions or serious side effects. The goal of these exploratory research studies is to find genetic markers that will identify persons with impaired glucose tolerance and cardiovascular disorders who will have the best possible response to nateglinide and/or valsartan or to identify persons who will have fewer side effects in order to maximize the benefit of the study drugs. This is not a genetic testing project since we are not trying to identify genetic information to determine risk of diseases that are not present during the study, alter clinical care or make or change a diagnosis. This research study is focused on studying the role genes play in impaired glucose tolerance and cardiovascular disorders and the responses of subjects to nateglinide and valsartan as described below.

It is planned to study polymorphisms in genes that are linked to the etiology of impaired glucose tolerance and cardiovascular disorders, those related to drug action, and those in drug metabolism genes, including any not yet currently identified, that may become important in the future as the human genome project moves toward completion. Polymorphisms related to type 2 diabetes mellitus may include Gly40Ser in the glucagon receptor (GCGR) gene, Thr130Ile in the hepatocyte nuclear factor 4 alpha (HNF4 α) gene and Asn130Asn in the solute carrier family 2 member 4 (GLUT-4) gene. Variants in drug metabolism genes may include the A-209G in the promoter of CYP3A4 and Arg144Cys and Ile359Leu in CYP2C9. Polymorphisms related to cardiovascular disorders may include Glu298Asp in the endothelial nitric oxide synthase (eNOS) gene, I/D in the angiotensin I converting enzyme (ACE) gene, and Met325Thr and Thr174Met in the angiotensinogen (AGT) gene. Potential variants in the angiotensin receptor (AGTR1) include 3'UTR A1166C.

To obtain sufficient DNA for pharmacogenetic studies, a single 12 ml blood sample will be drawn at Visit 3 from each subject who agrees, in writing, to participate in pharmacogenetic evaluations. The blood is collected into two 6 ml plastic EDTA-containing tubes, which are gently inverted several times to prevent clotting. The tubes are transferred on the day of sampling by Express Mail at ambient temperature to the Central Laboratory. DNA extraction, relabeling, and storage at -70°C will be done by Covance. It is intended that only one 12 ml sample will be taken once from the patient for these studies. However, in the event of loss or damage to the original or missed withdrawal at Visit 3, subjects may be requested to provide another blood sample.

The extracted DNA is given a new unique bar-code number by Covance. The sample extraction information is transferred electronically into a secured Novartis database separate from the clinical trial database. The blood sample and any DNA derived from the sample may be stored for up to 15 years to research scientific questions related to nateglinide, valsartan, impaired glucose tolerance, diabetes mellitus, metabolic disorders, and cardiovascular disorders. This research study is focused on studying the role genes play in impaired glucose tolerance and cardiovascular disorders and the responses of subjects to nateglinide and valsartan. Since nateglinide and valsartan may be developed for other diseases, and Novartis may develop new drugs for impaired glucose tolerance, diabetes mellitus, and cardiovascular disorders, the genetic information and samples may be used for other impaired glucose tolerance, diabetes mellitus, cardiovascular disorder, nateglinide, and valsartan-related drug research and development. If the sponsor desires to expand from this restricted scope of research, the sponsor will first seek approval from the IRB/EC.”

At the end of the storage period, any remaining blood sample will be destroyed according to standard biohazard procedures. Any remaining DNA will be destroyed according to chemical waste disposal procedures.

Biomarker assessments

Insulin, pro-insulin and other predictors of diabetes and cardiovascular disease (e.g. high sensitivity C-reactive protein) will be measured in all subjects subsequently enrolled. The parameters to be measured would be restricted to those that would lead to a better understanding of the pathophysiology of diabetes and cardiovascular disease, prediction of the development of these conditions or responses to treatment. For these measurements 12 ml of blood will be obtained at baseline, 12 months and at the final visit. Plasma and serum aliquots will be frozen until the time of analysis.

